### 12.13 Conventions

The number of decimal places for raw data and calculated values are determined by an internal guideline. The presentation of target variables follows the SGS proderm style guide.

For frequency tables, only those categories for which there is at least one subject represented will be included in the tables, except the intention is the direct visual comparison between categories.

## 13 Preparation and control of program code

All SAS® Code used for statistical analysis is the responsibility of the trial statistician but may be delegated to a programmer. The statistical output programmed in SAS® version 9.4 is based on this SAP. All statistical analysis programs are subjected to a version control system so that changes in the program can be tracked. The output log files of SAS® are searched automatically for errors and these are written, if available, automatically into an additional file. The log and error file of the final analysis is saved.

Controlling of program codes and statistical outputs is done by a person responsible for quality control e.g., a 2nd statistician according to SOPs DMD\_MED\_1003\_000 "Analysis in medical trials" and 12STA006.

The control follows a standardized scheme, which can be extended if necessary. The results of the control are saved in a separate Excel document signed.

The primary statistician implements the control's observations, documenting all actions taken.

All program codes and statistical outputs will be controlled based on a risk assessment. The recommended quality control strategy will be examined, and its appropriateness verified until release.

## 14 Formats

Statistical outputs will be presented in British English. Fonts point sizes of at least 8 will be used.

Data presented in listings and tables will be formatted as follows:

- alphanumeric data will be middle justified
- numeric values and date values will be middle justified
- column heading will be aligned centre for alphanumeric data, for numeric values and date values
  - If local conditions make it necessary, the alignment of the headings and data may differ.

Units will be given in the column heading for numeric values where appropriate.

Any abbreviations in tables and figures will be explained in footnotes unless they are already specified in the abbreviation list of the report.

Values in the data listing will be presented as recorded in the (e)CRF, except technical variables. Technical variables are labelled with "tc\_" in the variable name in the (e)CRF and may not be shown in the data listing.

Estimated means and standard deviations for continuous or quasi-continuous variables will be printed to one more decimal place than the individual value of measurement. Percentage values will be printed with one decimal place.

All p-values will be given with four digits to the right of the decimal point. In case a rounded value of  $p=0.0000$  is computed by SAS®, ' $p<0.0001$ ' will be printed.

## 15 Changes from clinical investigational plan

No changes from Clinical Investigation Plan to SAP occurred.

## 16 Software utilized

Task	Software	Version
Sample Size Estimation	SAS® for Windows nQuery Advisor 5.0 or other	9.4 or higher
Statistical Analysis	SAS® for Windows	9.4 or higher
Clinical database	secuTrial®	6.5.0.6 or higher

## 17 Topline results

The topline results include:

- Allocation of subjects in the respective study populations (SP, FAS, PP)
- Statistical analysis of the primary endpoint (FAS and PP)
- Selection of secondary efficacy endpoint(s) to support the primary endpoint (FAS and PP\*)
  - Change from baseline in IELT with the 3% Benzocaine condom compared to the standard NRL Condom
  - Proportion of subjects who achieve an increase of 2 mins from baseline in IELT in the 3% benzocaine condoms compared to the standard NRL condom.
  - Proportion of subjects who achieve an increase of 3 mins from baseline in IELT in the 3% benzocaine condoms compared to the standard NRL condom.
  - Proportion of subjects who achieve an increase of 4 mins from baseline in IELT in the 3% benzocaine condoms compared to the standard NRL condom.
  - Proportion of subjects who achieve an increase of 2 mins from baseline in IELT in the 5% benzocaine condoms compared to the standard NRL condom.
  - Proportion of subjects who achieve an increase of 3 mins from baseline in IELT in the 5% benzocaine condoms compared to the standard NRL condom.
  - Proportion of subjects who achieved an increase of 4 mins from baseline in IELT in the 5% benzocaine condoms compared to the standard NRL condom.
- Counts and percentages of (S)AEs (SP)
- Description of events in conjunction with causality to the study, pattern, intensity and outcome of (S)AEs (SP)

\* Provided that the rule for sensitivity analysis from chapter 12.2 applies.

---

## Overview

The summary of the statistical analysis scheme is presented in the following table:

Target variables	Population	Graphs	Statistical methods
Disposition of subjects	SP	Flowchart	
Disposition of investigational products	SP	Flowchart	
Baseline characteristics	SP		
childbearing potential, ethnicity, physical examination	SP	--	Counts and percentages
Age, height, weight, BMI	SP	--	Descriptive statistics
Medical history	SP	--	Counts and percentages
Primary variable*	FAS*, PP**		
IELT with the 5% Benzocaine condom A		Bar chart	Descriptive statistics 95 % Confidence Intervals GLMM or Wilcoxon signed ranks test
Secondary variable(s)	FAS		
IELT with the 3% Benzocaine condom B	FAS**, PP**	Bar chart	Descriptive statistics 95 % Confidence Intervals GLMM or Wilcoxon signed ranks test
EMSEX Pleasure Scale for Test Condom A OR B against standard NRL condom	FAS**	--	Descriptive statistics 95 % Confidence Intervals GLMM or Wilcoxon signed ranks test
Patient Global Impression of Change (PGIC)	FAS**	--	Counts and percentages GLMM or Wilcoxon signed ranks test 95 % Confidence Intervals
Subject perceived questions	FAS**		Counts and percentages

Target variables	Population	Graphs	Statistical methods
Proportion of subjects who achieve an increase of 2 mins from baseline in IELT	FAS**, PP***	--	Descriptive statistics Counts and percentages GLMM or Wilcoxon signed ranks test 95 % Confidence Intervals
Proportion of subjects who achieve an increase of 3 mins from baseline in IELT	FAS**, PP***	--	
Proportion of subjects who achieve an increase of 4 mins from baseline in IELT	FAS**, PP***	--	
Total clinical failure rate	FAS**	--	Descriptive statistics Counts and percentages

\*: Confirmatory hypothesis testing

\*\*: No confirmatory hypothesis testing, part of secondary analysis

\*\*\*: Provided that the rule for sensitivity analysis from chapter 12.2 applies.

Additional tables and figures are acceptable for illustrative purposes. Additional statistical tests can be performed, if reasons are given in the final report. The corresponding p-values have to be interpreted purely descriptive in the context of an explorative data analysis.

Examples of crucial tables, listings and figures can be seen in Chapter 19.

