## 9.5 Statistical Analyses

All statistical analysis will be performed using SAS® version 9.4 or higher. For all endpoints, in the event that the assumptions underlying the parametric approach are violated, alternative non-parametric methods will be used.

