**For secondary endpoints**

All secondary endpoints will be evaluated based on comparing the 5% and 3% benzocaine condoms with the standard NRL condom. No adjustment for multiplicity is planned for the secondary endpoints, and so p-values will be interpreted with appropriate consideration of Type I error.

The secondary endpoints of the investigation are:

Change from baseline in IELT with the 3% Benzocaine condom compared to the standard NRL Condom, over a 4-week assessment period.

Proportion of subjects who achieve an increase of 2, 3, 4 mins from baseline in IELT in the 5% and 3% benzocaine condoms compared to the standard NRL Condom.

- The change from baseline IELT with the 3% benzocaine condom compared to the standard NRL condom will be evaluated using the same linear mixed model as for the primary endpoint. The difference in least square means and associated 95% CI will be calculated, with a p-value to assess statistical significance.
- The proportion of subjects who achieve an increase of 2, 3 or 4 mins from baseline in IELT (calculated from the mean across all intercourse episodes within a period) will be calculated

for each condom type. The proportion achieving an increase of 2, 3 or 4 mins will be compared for the 5% and 3% benzocaine condoms versus the standard NRL condom using a GLMM with marginal means under the assumption that the mean of the outcome variable (1=success or 0=failure) follows a binomial distribution. Factors in the model will include fixed effects for treatment and period, and baseline IELT as a covariate. Subject will be included as a random effect. Comparison between the 5% and 3% Benzocaine condoms with the standard NRL condom will be expressed as an odds ratio, with an associated 95% CI and p-value.

A measure of Patient Global Impression of Change (PGIC) at the end of each 4-week assessment period, in subjects using the 5% and 3% benzocaine condoms compared to the standard NRL Condom.

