95 % confidence intervals	
For the analysis of the IELT with the 5% Benzocaine condom versus the standard NRL condom, 95% confidence intervals and an associated p-value are calculated. The calculation is done for each estimator of each time point separately for each condom group.
 
For the proportion of subjects in the total collective who achieved increase of 2, 3, 4 mins, comparison between the 5% and 3% Benzocaine condoms with the standard NRL condom will be expressed as an odds ratio, with an associated 95% CI.
 
For the analysis of PGIC, the comparison between the 5% and 3% Benzocaine condoms with the standard NRL condom will be expressed as an odds ratio, with an associated 95% CI.
 
For the descriptive analysis of EMSEX pleasure scale the 95%-CI will be displayed.
 
95%-Hodges-Lehmann-CI in case a GLMM-approach fails.

---------------------------	--

Sensitivity analysis of selected secondary endpoints	
In case of a relevant discrepancy between the sample size of the FAS and the PP population, a sensitivity analysis will be performed on the per protocol (PP) population, which will include data from subjects being compliant with the protocol.
 
The following rule is applied:
 
If the sample sizes of the FAS and PP populations differ by at least 10%, the following endpoints will be analysed on the basis of the PP population.
 
 
1) Proportion of subjects who achieve an increase of 2 mins from baseline in IELT in the 3% benzocaine condoms compared to the standard NRL condom.
 
2) Proportion of subjects who achieve an increase of 3 mins from baseline in IELT in the 3% benzocaine condoms compared to the standard NRL condom.
 
3) Proportion of subjects who achieve an increase of 4 mins from baseline in IELT in the 3% benzocaine condoms compared to the standard NRL condom.
 
4) Proportion of subjects who achieve an increase of 2 mins from baseline in IELT in the 5% benzocaine condoms compared to the standard NRL condom.
 
5) Proportion of subjects who achieve an increase of 3 mins from baseline in IELT in the 5% benzocaine condoms compared to the standard NRL condom.
 
6) Proportion of subjects who achieve an increase of 4 mins from baseline in IELT in the 5% benzocaine condoms compared to the standard NRL condom.
 
 
Clinically relevant differences between the results of the FAS and the PP analysis are highlighted and discussed.

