## 12.12 Confidence intervals

Confidence intervals (CI) for means are given where suitable. They are computed two-sided based on asymptotic normality at a confidence level of 95 % = 100 · (1 - α) %, if not stated otherwise:

$$CI = \mu \pm c \cdot \frac{\sigma}{\sqrt{n}}$$

for  $\mu$  = Sample mean for the respective variable

$c = t_{\alpha, 1-\alpha/2, n-1}$  Percentile of the t distribution

$\sigma$  = Sample standard deviation for the respective variable

$n$  = Sample size

Confidence intervals (CI) for odds ratio are given where suitable. They are computed two-sided based on asymptotic normality at a confidence level of 95 % = 100 · (1 - α) %:

This calculator uses the following formulae to calculate the odds ratio (or) and its confidence interval. or = a · d / b · c, where:

- a is the number of times both A and B are present,
- b is the number of times A is present, but B is absent,
- c is the number of times A is absent, but B is present,
- d is the number of times both A and B are negative.

Contingency table	A	1	0	Marginal sum
B				
1		a	b	a+b
0		c	d	c+d
Marginal sum		a+c	b+d	a+b+c+d

To calculate the confidence interval, we use the log odds ratio

$$\log(or) = \log(a \cdot d / b \cdot c)$$

with its standard error

$$SE(\log(or)) = \sqrt{\frac{1}{a} + \frac{1}{b} + \frac{1}{c} + \frac{1}{d}}$$

The confidence interval is calculated as:

$$CI = \exp(\log(or) \pm Z_{\alpha/2} \cdot \sqrt{\frac{1}{a} + \frac{1}{b} + \frac{1}{c} + \frac{1}{d}})$$

where  $Z_{\alpha/2}$  is the critical value of the normal distribution at  $\alpha/2$  (e.g., for a confidence level of 95%, the type I error is,  $\alpha = 0.05$  and its critical z-value is  $Z = 1.96$ ).

Note: The logarithms included in the formulae above are natural logarithms, i.e., log base e, sometimes denoted as  $\ln()$ .

Confidence Intervals for Wilcoxon signed rank test are calculated according to Hodges-Lehmann. This is done according to the following method:

Let  $[\lambda_*, \lambda^*]$  be the exact  $100 \cdot (1 - \alpha)\%$  confidence interval for the median difference. Let  $M = \frac{N(N+1)}{2}$

and let  $A_{[1]} \leq A_{[2]} \leq A_{[...]} \leq A_{[M]}$  be the  $M$  averages,  $\frac{(d_i + d_j)}{2}$  for all  $i \leq j$ , sorted in ascending order.

The lower confidence interval is formed by setting  $\lambda_* = A_{[i]}$  where  $[i] = 1 + t_*$  where  $t_*$  rounds down  $t_*$  to the nearest integer.

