The upper confidence interval is formed by setting  $\lambda^* = A_{[i]}$  where  $[i] = t^*$  where  $t^*$  rounds up  $t^*$  to the nearest integer.

$t_*$  is determined by finding a value for  $t_*$  so that the formula satisfies the following condition:

$$\Phi \left( \frac{t_* - \frac{N \cdot (N+1)}{4}}{\sqrt{\frac{N \cdot (N+1) \cdot (2N+1)}{24}}} \right) = \frac{\alpha}{2}$$

$t^*$  is determined by finding a value for  $t^*$  so that the formula satisfies the following condition:

$$1 - \Phi \left( \frac{t^* - \frac{N \cdot (N+1)}{4}}{\sqrt{\frac{N \cdot (N+1) \cdot (2N+1)}{24}}} \right) = \frac{\alpha}{2}$$

The confidence intervals for the proportion values are calculated according to the Wilson Score method. The following calculation method is used for this purpose:

$$CI = \frac{1}{1 + \frac{c^2}{n}} \cdot \left( \hat{p} + \frac{c^2}{2n} \pm c \cdot \sqrt{\frac{\hat{p} \cdot (1 - \hat{p})}{n} + \frac{c^2}{4n}} \right).$$

For  $c = \phi^{-1} \cdot (1 - \frac{\alpha}{2})$  where  $\frac{\alpha}{2}$  is the two sided error level and  $\phi^{-1}$  denotes the quantile function of the standard normal distribution, i.e. the inverse function of its distribution function  $\Phi$ .

$\hat{p}$  denotes the estimated proportion value.

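### If the GLMM fails, the SAP's Hodges-Lehmann interval cannot describe the 2-, 3- and 4-minute responder endpoints (minor)

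*SAP*

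**What the plan says.** The detailed responder text (SAP 11.4, secondary endpoints; Protocol 9.5.2.1) scores each man 1 or 0 on each condom and fits a binomial GLMM with treatment, period, baseline IELT and a random subject effect. The result is an effect on the odds scale: "Comparison between the 5% and 3% Benzocaine condoms with the standard NRL condom will be expressed as an odds ratio". That text names no fallback.

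The fallback comes from other places:

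- The SAP Overview table gives the responder rows "Descriptive statistics Counts and percentages GLMM or Wilcoxon signed ranks test 95 % Confidence Intervals". The cell is printed against the 2-minute row. The 3- and 4-minute cells are blank and are read here as merged with it.
- SAP 12.3, in the block on confidence intervals that also covers the responder proportions, ends with "95%-Hodges-Lehmann-CI in case a GLMM-approach fails". It is not limited to continuous endpoints.
- SAP 12.12 says "Confidence Intervals for Wilcoxon signed rank test are calculated according to Hodges-Lehmann". It builds the limits from the sorted averages of all pairs of within-subject differences, at ranks from a normal approximation. It has no rule for zero differences.
- Protocol 9.5 is broader and less specific: "For all endpoints, in the event that the assumptions underlying the parametric approach are violated, alternative non-parametric methods will be used".

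SAP 12.12 also says "The confidence intervals for the proportion values are calculated according to the Wilson Score method", but the formula is for one proportion, not for a paired comparison.

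**The concern.** The Hodges-Lehmann method estimates a shift between two measurements on a continuous scale, and SAP 12.12 itself describes the interval as one for the median difference. With a 0/1 response there is no shift to estimate. Most men will usually have a difference of zero, and the rest have -1 or +1. The interval then falls on a coarse grid that has no direct link to the difference in responder rates, and the result leaves the odds-ratio scale that the plan promised.

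The responder proportions serve a stated secondary objective and are listed in SAP 17 among the topline results that support the primary endpoint. If the fallback were used, a clearly significant paired test could stand beside an interval of exactly 0 to 0, or beside an estimate of a 100-point difference.

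**Working it through.** **1. Number of pairs.** The plan's own figure comes first. Inputs from SAP 12.7: SD 7.1, correlation 0.5, difference 2 minutes, 90% power, two-sided 5%, paired t-test. The SD of the paired difference is sqrt(2 × 7.1² × (1 − 0.5)) = 7.1. The normal approximation gives 133 and the exact paired t calculation gives 135 (power 90.1%); 135 / 0.9 = 150. Both stated figures are reproduced, and 135 is used below as the number of pairs. The plan gives no responder rates, so every split below is an assumption.

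**2. Values that can occur.** Each difference d is -1, 0 or +1, so every average (d_i + d_j)/2 is -1, -0.5, 0, 0.5 or 1. The limits are two of these averages, so they can take no other value. This needs no assumption.

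**3. Ranks under SAP 12.12, N = 135.** The number of averages is 135 × 136 / 2 = 9,180. The centre is 135 × 136 / 4 = 4,590 and the SD is sqrt(135 × 136 × 271 / 24) = 455.3. The cut points are 4,590 ± 1.96 × 455.3 = 3,697.6 and 5,482.4. The lower limit is therefore average number 3,698 and the upper is number 5,483. The estimate is the median, between numbers 4,590 and 4,591.

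**4. Assumed split: 30 respond only on the 5% condom, 10 only on control, 95 the same on both.**

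| Average | Count | Positions |
|---|---|---|
| -1 | 10 × 11 / 2 = 55 | 1 to 55 |
| -0.5 | 10 × 95 = 950 | 56 to 1,005 |
| 0 | 95 × 96 / 2 + 30 × 10 = 4,860 | 1,006 to 5,865 |
| 0.5 | 30 × 95 = 2,850 | 5,866 to 8,715 |
| 1 | 30 × 31 / 2 = 465 | 8,716 to 9,180 |

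Positions 3,698, 4,590 and 5,483 all fall on 0. Result: 0, interval 0 to 0.

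**5. Same data, zero differences dropped, N = 40.** There are 820 averages; the centre is 410 and the SD is sqrt(40 × 41 × 81 / 24) = 74.4. The limits are averages number 265 and 556. The averages are 55 at -1, 300 at 0 (to position 355) and 465 at 1. Result: 1, interval 0 to 1.

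**6. Paired-binary methods on the same data.** Difference (30 − 10)/135 = 14.8 points. Simple Wald standard error sqrt(40 − 20²/135)/135 = 0.0451, giving 6.0 to 23.7 points. Conditional odds ratio 30/10 = 3.0. Exact McNemar p = 0.0022. The signed-rank p-value (normal approximation) is 0.0016. All non-zero differences have the same size, so the signed-rank test reduces to the sign, or McNemar, test.

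**7. A larger assumed split, 45 versus 5 (29.6 points).** Zeros kept: 0.5, interval 0 to 0.5. Zeros dropped: 1, interval 1 to 1.

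**8. All 9,316 splits of 135 pairs, zeros kept.** The estimate is 0 for observed differences anywhere up to ±40.7 points, 0.5 for 23.0 to 70.4, and 1 for 42.2 to 100, with mirror values when control does better. Ties give ±0.25 in 10 splits.

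**9. Coverage as an interval for the difference in proportions.** Assumed control rate 20%, latent correlation 0.5, 4,000 simulated trials, zeros kept. The nominal 95% interval covered the true difference in 2% of trials at 10 points, 21% at 15, 63% at 20, 86% at 30 and 17% at 40.

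**The case against.** Several objections stand.

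A reader might infer from the Overview that the GLMM and the Wilcoxon test are a free choice. They are not: SAP 12.3 brings in the Hodges-Lehmann interval only when the GLMM fails, so the GLMM comes first.

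A reader might also infer that the whole fallback is worthless. It is not. The p-value is valid. The mock Wilcoxon table in SAP 19.2 has columns for the number of pairs, the numbers with negative and positive differences, and the mean difference. For 0/1 data these are the discordant counts and the paired difference in proportions. That table is titled for comparisons of assessment times, though its column headers allow products, and it has no Hodges-Lehmann column. Only the estimate and interval from 12.12 are at fault.

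Nor is the output unrelated to the true difference: it steps up as the difference grows and turns negative when control does better.

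The link to the responder endpoints is also thin. It rests on one summary cell and an unattached line in 12.3. Protocol 9.5 asks only for non-parametric methods, which would admit McNemar, and the Overview allows additional tests if reasons are given.

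Finally, the loss of the period term and of men without both condoms is not special to Wilcoxon, since exact McNemar has it too.

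None of this makes the stated interval usable. The SAP names it, leaves the handling of zeros open, and names no other interval for this paired comparison.

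**Conclusion.** The point holds and is minor. As written, the interval attached to the fallback for the responder endpoints cannot estimate a difference in proportions or an odds ratio. In the assumed 30 versus 10 split it reads either 0 to 0 or 0 to 1, for an observed difference of 14.8 points.

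The grid of possible limits follows from the 0/1 coding alone. The examples and the coverage figures rest on assumed splits, rates and correlation. Including the 3- and 4-minute endpoints rests on reading their blank Overview cells as merged.

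The harm is conditional on GLMM failure. In 120 simulated trials of 135 men at the 4-minute threshold, a maximum-likelihood random-intercept logistic fit was stable every time, so failure is probably rare under those assumptions. The endpoints are secondary and marked non-confirmatory, and the primary comparison is untouched.

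**What to change.** In SAP 12.3, 12.12 and the Overview, state that the Hodges-Lehmann estimate and interval do not apply to the 0/1 endpoints. State the fallback instead: if the binomial GLMM does not converge, use conditional logistic regression stratified by subject, with treatment and period, which keeps the odds-ratio scale. Use exact McNemar if discordant pairs are few. In either case, report the paired difference in proportions with a score-type 95% interval. Fill in the 3- and 4-minute Overview cells so that the scope is explicit.

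The cost is a few lines of SAP text and one standard procedure, with no change to data collection. The downside is small: exact McNemar drops the period term and men without both condoms, and conditional logistic regression uses only men whose outcomes differ between condoms.
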